Pre-operative treatment with DigiFab to prevent post-operative acute kidney injury (AKI) in patients at high risk for AKI undergoing cardiac bypass graft surgery

April 24, 2022

NCT # HP-00083553

1. Introduction

Acute kidney injury (AKI) occurs in up to 30% of patients undergoing coronary artery bypass graft (CABG) surgery¹; consequently, renal replacement therapy is often required. In patients needing renal replacement therapy, mortality is as high as 60-70%². There has been a trend to operate on higher risk patients³, likely increasing the prevalence of AKI post CABG. With roughly four hundred thousand CABG surgeries performed annually in the US⁴, this represents an enormous health care problem. Currently, there is no known therapy for AKI or way to prevent AKI occurrence in this patient population. Evidence suggests that elevated preoperative circulating endogenous ouabain (EO), a cardiac glycoside structurally similar to digoxin, leads to increased risk of AKI post CABG^{5,6}. We propose to study the impact of giving preoperative DigiFab, a biological preparation approved by the FDA for the treatment of digitalis toxicity, as a means to reduce/prevent the incidence of CABG-evoked AKI. DigiFab is expected to have a beneficial and possibly unique utility in this scenario because the antibodies it contains have the side-property of also binding EO with high affinity ([name] & [name], unpublished).

2. Rationale

Postoperative AKI is one of the most clinically significant causes of morbidity and mortality in patients undergoing CABG.³ Even minimal increases in serum creatinine are associated with increased mortality⁷. Similarly, acute renal failure is the strongest risk factor for death in patients undergoing cardiac surgery⁸. Clinical studies indicate that high pre-op plasma EO concentrations

are a marker for AKI in patients undergoing CABG surgery, and the highest plasma EO concentrations are associated with the highest risk and poorest clinical outcomes^{5,6}.

High plasma EO may directly cause renal damage in vivo and in vitro^{5,9}. In cultured rodent renal cells, prolonged ouabain treatment has been shown to decrease nephrin expression (a protein involved in formation of the glomerular filtration barrier).⁵ In vivo, prolonged ouabain administration decreases renal clearance, increases plasma creatinine, and increases proteinuria. Further, Rostafuroxin, a unique, first generation ouabain receptor antagonist, has been shown to attenuate the ouabain-evoked renal damage by preventing nephrin down regulation in rats^{9,10}. Unfortunately, Rostafuroxin is not currently an FDA approved drug, and the commercial prospects for this agent seem minimal because it binds to its in vivo ouabain receptor with relatively low affinity¹¹.

The absence of a clinically-useful ouabain receptor antagonist with which to interfere/preempt AKI opens the door to other strategies, including the possibility of short-term in vivo immunoneutralization. In this regard, DigiFab is one of several biologicals approved for the treatment of digitalis toxicity worldwide. In the US, DigiFab (BTG, Intl.), which consists exclusively of monovalent Fab fragments, was preceded by the divalent Fab preparation, Digibind (Wellcome, Glaxo, Smith Kline). Digibind is no longer commercially available. Both Fab preparations bind and immunoneutralize digoxin as well as other digitalis-like entities, including ouabain, with high affinity^{12,13}, but differ in the rates at which their Fab fragments are cleared from the circulation. Like Digibind, DigiFab has proven to be safe and has negligible side effects and virtually no toxicity when used at approved doses.¹⁴

Furthermore, several trials using Fab fragment preparations have been conducted recently. Among pregnant women with severe pre-eclampsia, both Digibind and DigiFab significantly reduced progression of renal dysfunction^{15,16}. The utility of these preparations in pregnant women with severe pre-eclampsia provides further evidence of safety as well as efficacy in minimizing the decline in renal function.

Based upon the aforementioned preliminary information, we will test the hypothesis that the ability to lower serum EO by immunoneutralization with DigiFab prior to CABG surgery will reduce the incidence of post-operative AKI, and thus, reduce post-operative morbidity and mortality.

3. Methods

We plan to conduct a randomized double-blinded study investigating the role of DigiFab in patients with elevated risk of acute kidney injury undergoing CABG surgery. Patients who are undergoing CABG, meet the inclusion criteria, and provide consent will be enrolled in this study and randomized to either DigiFab arm or the placebo (vehicle) arm. The number of patients to be consented will be enough to achieve two hundred and fifty evaluable participants. The number consented will not be more than 350 patients. The study involves a follow up period of 72 hours post CABG surgery.

3A- Recruitment

All patients awaiting non-emergency CABG surgery will be considered for this study. Patients with high risk of developing AKI post CABG will be included in this study. High risk of AKI will be defined as one of the following: GFR >15 but below 60 (must be >36 hours after receiving any contrast, but within two weeks of signing consent) or a history of diabetes mellitus. Diabetes will be defined as a past diagnosis or a current hemoglobin a1c of \geq 6.5%.

3B. Inclusion Criteria

Each patient must meet all the following criteria to be enrolled in this study:

- Patient provided informed consent
- Male or female > 18 years of age
- Undergoing CABG and one of the following:
 - GFR (Cockcroft-Gault) less than 60 (should be > 36 hours after receiving any contrast, but within two weeks of signing consent)
 - o Past diagnosis of Diabetes or current Hemoglobin A1c of \geq 6.5%

3C . Exclusion criteria

A patient who meets any of the following criteria will be excluded from this study:

- AKI defined as:
 - o Decrease in GFR > 25% of baseline based on RIFLE criteria¹⁷
- Received contrast within the past 36 hours of IP administration
- Prior kidney transplantation
- Prior adverse reaction to DigiFab
- Received Digoxin within the past 30 days

- Has allergy to papaya, papain, or sheep proteins
- GFR < 15 (within two weeks of signing consent and > 36 hours after receiving contrast)

Calculation of Creatinine Clearance (Ccr; Cockcroft-Gault Formula)

 $C_{Cr} = \{((140 - age) \times weight)/(72xS_{Cr})\} \times 0.85 \text{ (if female)}\}$

 C_{Cr} (creatinine clearance) = mL/minute

Age = years; Weight = kg

SCr (serum creatinine) = mg/dL

3D. Enrollment and Baseline

Patients awaiting surgery in the hospital or having elective surgery and initially seen as outpatients will be eligible for this study.

After a participant completes the consent process and is deemed eligible for this study, baseline parameters will be obtained. Laboratory tests—including basic metabolic panel (BMP, including serum creatinine), NT-pro-BNP (N-terminal prohormone of brain natriuretic peptide), and troponin—and hemodynamics – heart rate, blood pressure (systolic, diastolic, and mean arterial pressure)—obtained ideally within 24 hours before IP administration will be recorded. If multiple values exist within this time frame, the value closest to time of surgery will be used. Blood for EO concentrations, Proenkephalin A,¹⁸ and TIMP × IGFBP7^{19,20,21} will be drawn prior to investigational drug administration. Patient characteristics including age, sex, comorbidities (hypertension and diabetes) will be noted. Of note, ouabain concentrations take many days to return and will not be known prior to CABG.,

3E. Randomization

After ensuring eligibility, patients will be randomized by the investigational pharmacy. Stratified randomization will be employed using race and sex. Patients will be randomized approximately 24 hours prior to surgery. In the event that surgery is postponed to a later date, patients will be permitted to remain in the study. Digifab will be re-administered according to the usual protocol. If surgery is moved a second time and Digifab had been given, patients will be removed from the study.

3F. Intervention

BTG will provide DigiFab; placebo (saline) will be provided by the pharmacy. In-hospital study patients will be dosed intravenously with 80 mg Digifab or an equivalent volume of fluid the night prior to surgery (approximately 12-15 hours prior to surgery) and again 1 hour preoperatively. The vials will be stored in the hospital investigational pharmacy. Patients being admitted to the hospital on the day of surgery will receive 80 mg Digifab or an equivalent volume of fluid approximately 1 hour prior to surgery.

3G. Post-operative data:

We will collect blood for endogenous ouabain, Proenkephalin A, and TIMP × IGFBP7 in the immediate post-operative period 0 to 4 hours post-surgery. The ouabain measurement at this time will determine the fraction that is free and that which is bound to DigiFab. This 4 hr post-op sample window provides the only opportunity to obtain critical information concerning the efficacy of the DigiFab immunoneutralization. Total serum ouabain, Proenkephalin A, TIMP × IGFBP7, and creatinine concentrations will also be obtained at 72 +/- 12 hours post-surgery.

Time spent on cardiopulmonary bypass will be noted. Seven days post-operatively, need for any type of renal replacement therapy will be recorded. Lastly, mortality within a seven-day period will be noted.

3H. Data collection

Each variable will be captured and stored in a HIPAA compliant and secure database.

31. Primary endpoint: Changes in GFR will be compared in patients who receive placebo and intervention by ANOVA and, as appropriate, parametric or non-parametric tests. The primary endpoint will compare only patients with the 50% highest baseline (preoperative) concentrations of ouabain.

3J. Secondary endpoints:

- 1. Comparing GFR amongst all patients
- 2. Incidence of AKI comparing the groups (25% decrease from baseline)
- 3. Incidence of renal replacement therapy by 30 days
- 4. Comparing intraoperative and 30 day mortality for placebo vs DigiFab.
- 5. In patients on cardiopulmonary bypass for the longest time (top 50%).
- 6. Comparison of change in Proenkephalin A in patients receiving Digifab and placebo.
- 7. Comparison of change of TIMP × IGFBP7 in patients receiving Digifab and placebo.
- 8. Comparison of GFR in patients receiving one dose and patients receiving two doses of Digifab.

3K. Analysis

Mean comparisons will be made by ANCOVA and, as appropriate, parametric or non-parametric tests. Chi square will be used as indicated. We will control for GFR and sex.

3L. Power

We postulate that the average patient will have a GFR of 50 which correlates to a creatinine of 129 μ mol/l. Previous studies have shown a post-operative mean increase of 48 μ mol/l with a standard deviation of 76. Therefore, on average, post-operative creatinine should be 177 μ mol/l, which is roughly a GFR of 35. A trial of 62 patients per group (top half of elevated ouabain concentrations) should have a power of >70% to detect a 36 μ mol/l difference in plasma creatinine, i.e., a creatinine of 141 μ mol/l (177-36). A creatinine of 141 μ mol/l correlates to a GFR of 45—a ~25% increase in GFR.

4. Risks

The primary risk associated with this study includes all of the potential adverse effects of DigiFab including: anaphylactic and anaphylactoid reactions, delayed allergic reactions, and a febrile response to immune complexes formed. However, since the Fab fragment of the antibody lacks the antigenic determinants of the Fc region, this should pose a reduced immunogenic threat. Of note, no patients during the clinical trials experienced an anaphylactic event. Patients with allergies to sheep protein would be at particular risk. In a registry of 717 adult patients receiving DigiFab, 6 had a probable or possible adverse reaction to the medication. All were symptomatically treated successfully²². Study participants will be monitored closely for potential adverse effects in the perioperative, operative, and post-operative setting. If an anaphylactic

reaction occurs, epinephrine, steroids, an H2 blocker, and diphenhydramine will be given as appropriate. Each blood draw carries the risk of pain associated with the venous puncture. As this is the first use of DigiFab in this patient population, unknown side effects are possible.

Data Safety and Monitoring Board

There will be an independent Data Safety and Monitoring Board (DSMB) which will assess the safety of the trial after 62 patients (first 25% of patients are enrolled). An unblinded coordinator will provide the board with all adverse events and deaths to investigate. The DSM board will evaluate the cause of deaths and allergic reactions. The panel will consist of [name], [name], [name], and a statistician.

5. Benefits

Study participants may experience short and long-term benefits. Potential benefits include prevention of AKI, reduced hospital stay, protection from renal replacement therapy, and decreased mortality. In the long term, potential benefits include protection from: progression to chronic kidney disease, need for renal replacement therapy and early death.²³

6. Confidentiality

All data collected will be de-identified once stored on the database.

7. Consent process

Study participants who meet inclusion criteria will be approached by a study coordinator or investigator. The consenter will review the risks and benefits to partaking in this trial. If the

participant expresses interest, a study consent form will be provided. Potential participants will have the opportunity to ask questions at any point during the explanation process.

8. Conflict of Interest

Drs. [name], [name], and [name] have a provisional patent and a patent pending for the use of DigiFab (and/or a ouabain antagonist) to prevent renal dysfunction in patients undergoing CABG. All investigators will be blinded to the treatment received until all data are finalized.

9. HIPAA Compliance

All authors have completed HIPPA training in accordance with the University of Maryland.

10. Stopping Rules

The study will be halted if the independent data monitoring determines that known or unknown side effects of DigiFab are occurring with unacceptable symptoms for the patient and/or mortality. The DSMB will determine the specific rules.

11. Timeline

- 1. Patient consent and enrollment
- 2. Prior to administering the first dose of DigiFab, draw blood for NT-pro-BNP, troponin, proenkephalin A, TIMP × IGFBP7, and endogenous ouabain (ideally within 24 hours of IP administration. Record BMP (including creatinine) values, demographics, and hemodynamics.

- **3. For hospitalized patients,** approximately 12-15 hr before surgery: Administer DigiFab 80 mg or placebo if > 36 hours post contrast. If necessary to meet entry requirements, only immediate pre-op dose will be given.
- **4.** One hr pre-op: Administer a second dose (or first dose for same day admissions) of DigiFab 80 mg or placebo
 - **5.** Surgery
- **6.** 0-4 hr Post-op: Draw blood for free and bound ouabain, proenkephalin A, TIMP × IGFBP7 determinations. Record BMP (including creatinine) values
- 7. 72 ± 12 hr post-op: Draw blood for total ouabain, proenkephalin A, TIMP × IGFBP7. Record BMP values (including creatinine).

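### Diabetes and planned admission route are left out of the 3K adjustment, which costs the primary comparison a modest amount of precision and of protection against chance imbalance

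*Combined protocol and SAP*

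**What the plan says.** - **Randomisation (3E).** "Stratified randomization will be employed using race and sex". On timing: "Patients will be randomized approximately 24 hours prior to surgery".
- **Regimen (3F).** In both arms, in-hospital patients are infused "the night prior to surgery (approximately 12-15 hours prior to surgery) and again 1 hour preoperatively". For the others, "Patients being admitted to the hospital on the day of surgery will receive 80 mg Digifab or an equivalent volume of fluid approximately 1 hour" before surgery. In-hospital patients are therefore planned for two infusions and same-day admissions for one.
- **Exception (section 11, item 3).** For hospitalised patients with recent contrast: "If necessary to meet entry requirements, only immediate pre-op dose will be given".
- **Entry risk (3A, 3B).** A patient qualifies through reduced GFR or through diabetes.
- **Baseline record (3D).** "comorbidities (hypertension and diabetes) will be noted". Admission route is not among the baseline variables listed.
- **Adjustment (3K).** Means are compared by ANCOVA: "We will control for GFR and sex". Section 3I names ANOVA for the primary endpoint.
- **Elsewhere.** Number of doses appears only in secondary endpoint 8. Diabetes is used in no analysis.

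**The concern.** The protocol singles out both factors. It uses diabetes to define high risk of AKI. Admission route largely sets how many infusions a patient is assigned, and it also separates patients already waiting in hospital from those who come in for elective surgery. It is reasonable to expect either factor to be related to the change in renal function.

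A prognostic baseline factor that is neither balanced by design nor in the model has two effects. Its variation stays in the error term, and the estimate carries any chance difference between the arms. The primary set is only the upper half by baseline ouabain, about 62 per arm, and planned power is stated as only a little over 70%. Settling the covariates now also avoids choosing them after an imbalance has been seen.

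**Working it through.** **Inputs.** From 3L: 62 per group, a difference of 36 µmol/l in creatinine, SD 76 µmol/l. From 3 and 3I: 250 evaluable patients, of whom the upper half by ouabain are analysed, so 250/2/2 = 62.5 per arm. Assumed, because the documents do not state them: two-sided 5% test; factor prevalence 50%; a mean difference of 0.25 to 0.5 SD between the two levels of the factor (19 to 38 µmol/l).

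**1. The plan's own power.** The standard error of the difference is 76 × √(2/62) = 13.65 µmol/l, and 36/13.65 = 2.64. Power is 74.4% by the noncentral t with 122 degrees of freedom (75.1% by the normal approximation). The stated figure of more than 70% reproduces, so there is no arithmetic error here.

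**2. Gain from adjustment.** A binary factor with prevalence p and a mean difference of d SDs explains R² = p(1 − p)d².

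| d (SD) | R² | Residual SD = 76√(1 − R²) | Power | Gain (points) |
|---|---|---|---|---|
| none | 0 | 76.0 | 74.4% | – |
| 0.25 | 0.25 × 0.0625 = 1.6% | 75.4 | 75.1% | 0.7 |
| 0.5 | 0.25 × 0.25 = 6.25% | 73.6 | 77.1% | 2.7 |

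This treats 76 as the SD left after GFR and sex, so R² means variance explained beyond those two terms. Using two degrees of freedom (122 to 120) lowers the 74.4% by about 0.01 point.

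**3. Size of chance imbalance.** The SD of the between-arm difference in a 50% factor is √(2 × 0.25/62) = 0.0898. The 95% range is 1.96 × 0.0898 = ±17.6 percentage points (±16.1 at a prevalence of 30% or 70%). The median absolute difference is 0.6745 × 0.0898 = about 6.1 points.

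**4. What that does to the estimate.**
- At the 95% edge: 0.176 × 19 = 3.3 µmol/l and 0.176 × 38 = 6.7 µmol/l. That is 9% to 19% of the 36 µmol/l target, or 0.24 to 0.49 standard errors.
- At the median: 0.061 × 19 = 1.2 µmol/l and 0.061 × 38 = 2.3 µmol/l, or 3% to 6% of the target.

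**5. Would strata do instead?** I simulated 250 patients in permuted blocks of four, assuming 50% prevalence for route and for diabetes, a 30/70 split by race and 25% women. With race and sex as strata, the arms differed by 10 points or more on route in 26.7% of primary sets. With route and diabetes added as strata, this still happened in 13.4%. Ouabain results are not available before surgery, so the primary set cannot be balanced directly and stratification carries over only in part.

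**The case against.** The strongest reply is that nothing here is an error. A randomised comparison is valid without these covariates, and its standard error already allows for chance imbalance. Even at the 95% edge the shift is under half a standard error. That stands, and a reader who infers that the primary result is biased goes further than the documents allow.

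The gain is also small and rests on an assumed prognostic effect. Section 3K already adjusts for GFR, and the entry rule ties GFR to diabetes: a patient with GFR of 60 or more must be diabetic, and a non-diabetic must be below 60. Baseline GFR may therefore already carry part of what diabetes would add. The power figures are in creatinine, as in 3L, while the primary endpoint is change in GFR. All of this stands. It limits how firmly the size can be stated, but it does not remove the low-cost gain.

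Three stronger readings are tempting and fail:
- **That a route term would stop the result averaging two regimens.** A main effect for route still leaves one averaged treatment effect. Separating the regimens would need an interaction or subgroup estimates. Endpoint 8 is the plan's only look at dose number.
- **That admission route alone fixes the number of infusions.** The section 11 exception lets some hospitalised patients receive only the pre-op infusion. For the same reason, route cannot be read back from the dosing record.
- **That more strata would be free.** Four binary factors make 16 cells for 250 patients, and the balance reaches the primary set only in part.

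It can also be said that age, hypertension or NT-pro-BNP, all recorded, have an equal claim. The choice does involve judgement. The case for these two is that the protocol itself uses one to define risk and the other to set the planned regimen.

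**Conclusion.** The point holds as a modest matter of precision and of protection against chance imbalance. Diabetes and planned admission route are missing from the adjustment, and no other section supplies them. If one factor explained 1.6% to 6.25% of outcome variance beyond GFR and sex, power would rise by about 0.7 to 2.7 points from about 74%. This rests on an assumed prognostic effect of 0.25 to 0.5 SD, 50% prevalence and a two-sided 5% test, none of which the documents give. It also assumes that planned route is known when patients are randomised about 24 hours before surgery, which is likely but not stated. The validity of the primary test is not in question.

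**What to change.** In 3K, prespecify two further ANCOVA terms beside GFR and sex: diabetes (yes/no, by the 3B definition) and planned admission route at randomisation (in-hospital or same-day). Apply them to the primary endpoint and secondary endpoint 1. For the primary endpoint, state that the 3K ANCOVA is the model that applies, since 3I names ANOVA. Use planned route rather than infusions received, so that the term is a true baseline factor. Leave the strata in 3E as they are.

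The cost is two degrees of freedom and one recorded field for planned route at randomisation. The field is needed because the dosing record cannot distinguish a same-day admission from a hospitalised patient limited to one infusion. Diabetes is already collected. Dosing and patient care do not change.

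### Section 3E removes randomised, already dosed patients after a second postponement, and no text keeps them in safety or 30-day follow-up

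*Combined protocol and SAP*

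**What the plan says.** Section 3E randomises patients about 24 hours before surgery. After a first postponement the patient stays in the study and "Digifab will be re-administered according to the usual protocol". After a second, the rule changes: "If surgery is moved a second time and Digifab had been given, patients will be removed from the study".

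The usual dosing is in section 3F: "In-hospital study patients will be dosed intravenously with 80 mg Digifab or an equivalent volume of fluid the night prior to surgery", "and again 1 hour preoperatively". Patients admitted on the day of surgery get one dose, about an hour beforehand.

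The analysis text does not mention removed patients. Section 3I says "Changes in GFR will be compared in patients who receive placebo and intervention by ANOVA" and "The primary endpoint will compare only patients with the 50% highest baseline (preoperative) concentrations of ouabain". Section 3 aims for 250 evaluable participants from at most 350 consented, without defining evaluable. Sections 3I to 3K define no analysis or safety population and give no missing-data rule.

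**The concern.** Stopping further dosing after two failed surgery dates is sensible. Ending participation is a different step, and the rule makes no distinction between them. A coordinator who follows section 3E as written could stop collecting data on a patient who has just had one or two courses of the product.

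Safety is mainly what is at stake. Section 4 says this is the first use of DigiFab in this population, that unknown side effects are possible, and that delayed allergic and febrile reactions are among the risks. The DSMB is to assess allergic reactions and deaths, and under section 10 it has still to set its stopping rules. Re-dosed patients carry the most information on repeat exposure.

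A lesser concern is efficacy. Excluding patients after randomisation can bias the comparison if the reason for the second move is related to the drug or to prognosis.

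**Working it through.** **1. The plan's power figure.** Inputs from section 3L: 62 per group, difference 36 µmol/l, SD 76. Two-sided 5% and equal allocation are assumptions, because the plan states neither.

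- Standard error = 76 x sqrt(2/62) = 13.65.
- 36 / 13.65 = 2.637, and 2.637 - 1.960 = 0.677.
- Power = Φ(0.677) = 75.1%, or 74.4% with the noncentral t.

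This agrees with the stated figure of more than 70%. Section 3 also leaves room for 350 - 250 = 100 consented patients who prove not evaluable. If removed patients count among these, they are replaced and the power stands.

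**2. Possible exposure at removal.** Inputs from sections 3E and 3F, for a patient in the DigiFab arm.

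| Case | Total dose |
|---|---|
| One dose given before the second move | 1 x 80 = 80 mg |
| Usual in-hospital course | 2 x 80 = 160 mg |
| Day-of-surgery admission, dosed before each move | 2 x 80 = 160 mg |
| In-hospital, both full courses given | 4 x 80 = 320 mg |

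The last row is the extreme. It needs both one-hour pre-operative doses to have been given, each followed by a move.

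**3. Does any text keep a removed patient under observation?**

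| Provision | Place | Covers a removed patient? |
|---|---|---|
| 72-hour follow-up and creatinine | 3, 3G, 11 step 7 | Counted from surgery; nothing is due if there is none |
| Seven-day renal replacement and death | 3G | Renal replacement is timed post-operatively; removed patients not mentioned |
| 30-day contact | 11 step 8 | General; does not say it survives removal |
| Adverse events and deaths to the DSMB | Section on the DSMB | Covers events before removal; silent on collection afterwards |
| GFR among all patients | 3J item 1 | Contrasts with the top ouabain half; does not define a randomised population |

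No entry overrides the removal rule.

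**4. Size of any efficacy bias.** In each arm, dropping patients shifts the mean by (share removed) x (mean of those kept - mean of those removed). The bias is the difference between the arms in that product. It is zero if removal is unrelated to arm or to outcome. The documents give neither the share twice postponed nor the outcome gap, so no value can be computed.

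**5. Which ouabain sample selects the primary population?** Section 3D says the blood "will be drawn prior to investigational drug administration", and section 11 step 2 places the draw before the first dose. For a re-dosed patient, a sample taken before the second course would follow treatment, so it should not decide membership of the top half. Step 2 already implies the right choice; it needs only to be made explicit.

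**The case against.** The best defence is that a blinded exclusion before surgery, of patients whose operation did not follow the dose, is a reasonable modified analysis set for a post-operative outcome. This largely stands for the GFR comparison. A patient operated on later without further product says little about neutralisation at surgery. Keeping such patients can also cost more power than dropping them. If 5% are affected (an assumption, probably above the true rate), power by the noncentral t is 72.2% when they are removed without replacement, and 70.0% when they are kept and that share of the DigiFab arm gets no benefit. Including them in the GFR analysis is therefore a trade-off.

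It is also true that adverse events before removal already go to the DSMB, and that 320 mg is an arithmetic extreme with no evidence that it would occur. Neither point covers observation after removal.

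A reader might infer more than the documents support:

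- **One-sided removal that reveals allocation.** Taken literally, only the DigiFab arm can meet the condition. But the preceding sentence in 3E and section 11 step 2 use the product name as shorthand for study product in general. The literal reading is unlikely and carries no weight here beyond a wording fix.
- **An as-treated primary analysis.** The verb in "Changes in GFR will be compared in patients who receive placebo and intervention by ANOVA" is ordinary wording for the arms, and section 3 defines randomised arms.
- **A numerical cap on bias from the registry in section 4.** The 6 reactions in 717 patients are a rate of adverse reactions. Surgery can be moved for other reasons, including prognosis, so this rate bounds nothing.
- **A damaged sample size.** Step 1 of the working shows that it is not.

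**Conclusion.** The point holds as a minor one. The plan has an explicit rule that takes randomised, dosed patients out of the study, and no text keeps them in safety or 30-day follow-up. Followed as written, it can lose data on repeat exposure of up to 320 mg in a first-use population.

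The number affected is unknown. Efficacy bias is probably very small. That judgement rests on removal taking place before surgery and on the likely reading that the rule is blinded and applies to both arms. It would fail only if second moves were related to the drug or to prognosis in a way that differs by arm, and the documents give no means of measuring that.

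**What to change.** In both section 3E sentences on postponement, write *assigned study product (DigiFab or placebo)*. Replace removal from the study with *receive no further study product*. Then add a short paragraph:

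- Adverse-event reporting to the DSMB continues, as does 30-day follow-up for death and renal replacement, counted from the last dose if there is no surgery. Report these outcomes in the assigned arm.
- Record the 72-hour creatinine if surgery takes place.
- Report by arm how many patients were twice postponed, and how many had no surgery or no post-operative creatinine.
- Show the GFR comparison with and without these patients, under the same rule in both arms.
- For the top-half ouabain selection, use the sample taken before the first dose.

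The baseline creatinine rule in section 3D ("If multiple values exist within this time frame, the value closest to time of surgery will be used") can stay. Going back to a value before the first dose could mean using a stale baseline after one or two postponements.

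The cost is two reworded sentences and one paragraph, with no extra patients. Staff must track a few rescheduled patients, though section 11 step 8 already allows 30-day status to come from hospital records. The downside is slight dilution in the GFR analysis that includes these patients, which is why both versions should be shown.
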